#### Confidential

The CLN-PRO-V006 Statistical Analysis Plan pre-specified the use of the Cox Proportional Hazards model to compare the secondary patency rates of HAV and ePTFE. The observed hazard ratio for loss of secondary patency at 18 months is 1.19, with lower and upper 95% confidence interval (CI) of 0.78 and 1.81, respectively. Since the observed upper 95% CI is greater than the non-inferiority margin, we failed to reject the null hypothesis, and therefore, could not establish non-inferiority of HAV relative to ePTFE.

However, given that the hazards for loss of secondary patency between HAV and ePTFE were not proportional (i.e., the curves for secondary patency cross near 400 days, making the relative risks of loss of patency non-proportional over time), the pre-specified Cox Proportional Hazards model is not ideally suited to analysis of the CLN-PRO-V006 secondary patency data. Therefore, a sensitivity analysis was performed using the non-parametric restricted mean survival time (RMST) method, which does not make assumptions regarding proportionality of hazards between the two arms of the trial. RMST estimates a gain or loss in the event-free survival time due to treatment versus control in a specified time period. The results from the RMST analysis indicated that the time to failure of secondary patency was delayed, on average, by 11 days in the HAV arm compared to the ePTFE arm at the 18 month time point, and non-inferiority of the HAV in comparison to ePTFE was demonstrated with this alternative RMST analysis.

The time to loss of primary patency was significantly shorter for the HAV than for ePTFE, with a hazard ratio of 1.89. Since losses of primary patency for the HAV seemed to briefly accelerate around 60 to 90 days, it is unclear the extent to which study-mandated ultrasounds at 60 and 90 days, combined with the lack of experience in managing the HAV at most study sites, may have triggered interventions on the HAV study conduit that would have led to a loss of primary patency at those times.

Information on access-related infections was collected for all study subjects. Table 3 provides the rates of access-related infections involving the study conduit (not local site infections, and not infections of tunneled dialysis catheters or other accesses). The HAV had significantly fewer study access-related infections than ePTFE (p= 0.041), with the absolute rate of infections for ePTFE roughly five times higher than HAV (4.76 vs. 0.97 infections per 100 subject years of dialysis use for ePTFE and HAV, respectively). Fewer HAV subjects required intravenous antibiotics for treating their access related infections. Markedly fewer HAV subjects required hospitalization for infection (13 vs. 3 instances of hospitalization for infection with ePTFE and HAV, respectively). Lastly, conduit removals were more frequent for ePTFE than for HAV.

Clinical Event	ePTFE (N = 178)	HAV (N = 177)	Total (N = 355)
Conduit Infections per 100 subject-years of dialysis	4.76	0.97	( p= 0.041)
Subjects Needing IV Antibiotics	15	9	24
Subjects Needing Hospitalization	13	3	18
Conduit Removals (partial and complete)	8	13	21

#### Table 3 Summary of Access-Related Infections in V006

ePTFE = expanded polytetrafluoroethylene, HAV = Human Acellular Vessel, IV = intravenous

#### 2.4.7. Human Acellular Vessel Host Response and Remodeling Data

Humacyte has been able to assess the general host response to the HAV in a number of human participants; this was accomplished through the microscopic examination of explanted HAV and adjoining tissue samples obtained during surgical revision procedures (Kirkton, 2019). The analysis (mostly of a section close to the venous anastomosis) included assessments of:

- Cellular infiltration of histotypic, inflammatory and immunological populations.
- Extracellular remodeling processes, including neo-synthesis and reorganization of ECM components that typically occur in native blood vessels.

In 16 cases, small segments of the HAV and adjacent vascular tissue were explanted, fixed in formalin solution and shipped to Humacyte for analysis. Implant duration ranged from 16 to 200 weeks.

In man, the HAV remodeled in a manner consistent with that observed in primate studies. There was infiltration of cell populations that are normally associated with angiogenesis and vascular organization and structure; namely, those with endothelial, smooth muscle and fibroblastic phenotypic characteristics were observed. Endothelial cells formed a monolayer on the luminal surface of the HAV. Migration of actin-positive smooth muscle cells into the wall of the HAV was consistently observed. A well-vascularized adventitial layer of non-constrictive fibrous tissue formed around HAV. Infiltration of the graft material by inflammatory and immunoreactive cell populations was either not evident or was mild and generally unremarkable. Degradation or breakdown of the implant was not observed.

Histotypic neo-synthesis and reorganization of the ECM was observed in patterns indicative of integration of the HAV into the host. An increase in the density of collagen type I, the main type of collagen found in the wall of native blood vessels, was apparent in the majority of HAV explant specimens. The structure of collagen type I in these specimens exhibited a more mature,

#### Confidential

organized pattern, with distinct fibers and a prominent circumferential alignment evident in explanted samples in comparison with pre-implant specimens. In some specimens, the fibrillar staining pattern of collagen III became more prominent and more organized, with a circumferential orientation. Fibronectin levels and staining patterns remained unchanged.

Cannulation sites within the HAV appeared to be repaired by the host in a fashion similar to wound repair in the body (Figure 1). In one case, an explanted specimen was tested for suture retention strength at the time of explant and exhibited a substantial increase over the pre-implant level.

#### Figure 1: Images of Mid-Vessel Segment Explanted at 11-Months Post-Implant

- A: Low magnification showing 3 cannulation sites (in dashed boxes),
- B: Fresh cannulation track,
- C: Cannulation track during remodeling
- D: Older cannulation track that has been repaired.

The image above shows a mid-vessel segment explanted at 11 months post-implant and shows several prior cannulation tracts from dialysis access. Figure 1B shows a very recent cannulation site with fresh clot extending into the tract from the lumen. Figure 1C and D show partially healed

cannulation tracts, with evidence of cellular repopulation extending in from the lumen. Remodeled cannulation tracks contain new collagen and a few micro-conduits.

In conclusion, the HAVs were remodeled by the host to form a vascular-like structure more similar to the histological appearance of native vasculature. The HAVs were repopulated by cell types that are characteristic of healthy native vasculature. Evidence of ECM remodeling processes, including neo-synthesis and reorganization of ECM components that typically occur in native blood vessels, were observed. The cellular infiltration and ECM remodeling patterns were indicative of the integration of the HAV into the host.

#### 2.4.8. Conclusions

Clinical experience indicates that the HAV remains mechanically strong over implantation periods of more than 60 months with no evidence of dilatation. The HAV profile includes use as a hemodialysis access in ESRD subjects, an arterial bypass conduit in PAD and vascular trauma subjects, and an interposition vessel in vascular trauma subjects. The benefit-risk for the HAV remains favorable in these subject groups and continued clinical development for these target indications is warranted. The SAE profile has been typical of that expected in the dialysis and PAD populations. In hemodialysis populations, secondary patency of the HAVs is substantially higher than the historical data for both ePTFE and AVF (accounting for non-maturation). In PAD, patency is in line with historical ePTFE and autologous conduit for above-knee bypass. No evidence of immunogenicity of the HAV has been found, and the HAV remains mechanically robust even after repeated puncture for hemodialysis and under high pressure, high outflow resistance in arterial reconstruction.

These data support the use of HAV in future Phase 2 and Phase 3 studies for vascular replacement and reconstruction in diseased or damaged (trauma) vessels.

## 2.5. Potential Risks and Benefits

#### 2.5.1. Potential Risks

It is anticipated that subjects participating in the study will be exposed to similar risks to those associated with other arterial conduits. Risks associated with the study investigational product may include but are not limited to:

- Thrombosis/occlusion of the conduit or host vessels, with consequent limb ischemia
- Embolism from a thrombosed conduit

- Bleeding and hematoma formation at the surgical site
- Infection at the surgical site or systemic
- Stenosis of the conduit or its anastomoses
- Aneurysm or pseudoaneurysm formation
- Swelling of the limb

Regular clinical examination of the HAV implantation site and assessment of the patency, blood flow and diameter using ultrasound during the study should allow early detection of complications and permit appropriate intervention including HAV explantation. CT angiography at Months 1, 6, 12 and 60 will allow the detection of anatomical abnormalities of the HAV such as localized dilation and intimal hyperplasia.

The HAV is grown using donor human aortic smooth muscle cells. The HAV is decellularized during manufacturing and thus consists of human ECM proteins. It is possible that the HAV may provoke an immune response which may lead to damage to the HAV and possible cross reactivity against host proteins. Possible antibody formation will be assessed by analyzing PRA.

#### 2.5.2. Potential Benefits

Patients who undergo implantation of the Humacyte HAV may benefit from a reduced number of infections and infection-related complications versus a conventional ePTFE or a Dacron graft. In addition, the risks listed in Section 2.5.1 typically encountered with conventional synthetic grafts may be decreased with the Humacyte HAV. Finally, the longevity (secondary patency) of the Humacyte HAV may be greater than that of conventional synthetic grafts.

#### 2.5.3. Risk-Benefit Rationale

The risks anticipated in this study are similar to those associated with currently marketed prosthetic grafts used for peripheral bypass surgery. The potential advantages of the HAV compared to currently marketed grafts may lead to a lower infection rate and reduced need for HAV replacement.

Recruitment will be restricted to a maximum of 25 subjects who receive implants to provide safety and efficacy data in the PAD population.

There is no formal hypothesis testing in this study, but data from the study will be compared with historical data on synthetic peripheral bypass grafts to assess the safety and efficacy of the HAV.

# 3. STUDY OBJECTIVES

## 3.1. **Primary Objectives**

This is an open label Phase 2 study. There is no formal hypothesis testing.

#### Safety:

• To evaluate the safety and tolerability of the Humacyte HAV in PAD patients undergoing femoro-popliteal bypass surgery

#### Efficacy:

- To determine the patency (primary, primary assisted and secondary) rate of the Humacyte HAV at Month 12
- To determine the incidence of hemodynamically significant stenosis (>70%) defined by duplex ultrasound, and the time to stenosis development

## 3.2. Secondary Objectives

#### Safety:

- To assess changes in the PRA response after HAV implantation
- To determine mechanical stability of the HAV based on freedom from aneurysmal degeneration on duplex ultrasound and CT imaging
- To determine HAV durability in terms of freedom from need for HAV explantation or replacement due to infection, bleeding or conduit degeneration

#### Efficacy:

- To determine the patency of the HAV (primary, primary assisted and secondary) at Months 3, 6 and 9
- To determine the rates of interventions needed to maintain / restore patency in the HAV through Month 12
- To assess effect of HAV implantation on symptoms of PAD using the VascuQol instrument
- To assess effect of the HAV on ABI
- To assess effect of the HAV on 6 minute walk test

# 4. STUDY DESIGN

# 4.1. Description of the Study Design

Prospective, multicenter, single arm, non-randomized Phase 2 study

## 4.2. Study Endpoints

Endpoints will be evaluated at multiple time points up to 60 months after HAV implantation. The primary analysis of the study will be conducted on the earlier of a) when the final subject enrolled reaches 12 months post-implant or b) all subjects enrolled in the initial 36 month accrual period have reached 12 months post-implant.

#### 4.2.1. **Primary Endpoints**

#### Safety:

- Incidence of HAV aneurysm formation (true or pseudo)
- Anastomotic bleeding or spontaneous rupture
- HAV infection
- HAV removal
- Significant local inflammation at the HAV implantation site
- Frequency and severity of adverse events

#### Efficacy:

- HAV patency rates (primary, primary assisted, and secondary patency rate)
- Hemodynamically significant stenosis (>70% by duplex ultrasound criteria)

#### 4.2.2. Secondary Endpoints

#### Safety:

- Change from baseline in PRA
- Change from baseline in hematology, coagulation, and clinical chemistry parameters

#### Efficacy:

- HAV interventions
- Patient reported PAD symptoms (VascuQol)
- ABI
- 6 minute walk test
- HAV remodeling at Months 1 (Day 29), 6 and 12 by CT angiography and US

#### 4.2.3. Long Term Endpoints (post Month 12 through Month 60)

- HAV interventions
- Evidence of aneurysmal dilatation or stenosis of the HAV on routine clinical duplex US
- Primary, primary assisted, and secondary patency at 18, 24, 30, 36, 42, 48, 54 and 60 months
- Limb salvage/amputation at 18, 24, 36, 48, and 60 months, for all subjects who have not died, withdrawn, or been lost to follow-up.
- Incidence of surgical revascularization of the implanted limb, at the level of the HAV or distal to HAV, for all patients who have not died, withdrawn, or been lost to follow-up.
- VascuQol PAD symptom assessment consists of 25 questions. The total score and the 5 domain scores (Activity, Symptom, Pain, Emotional, and Social) will be recorded in the clinical database, at 18, 24, 36, 48 and 60 months, for all patients who have not died, withdrawn, or been lost to follow-up.

# 4.3. Duration of Study Participation

For an individual subject, the expected duration of active study participation is approximately 61 months. Enrollment (accrual) is expected to occur over 36 months. Additional data on patient and HAV status will be collected at 6 month intervals through 60 months after HAV implantation.
# 5. STUDY POPULATION

# 5.1. Description of the Study Population

The study population will consist of patients with symptomatic peripheral vascular disease as evidenced by claudication, rest pain or critical limb ischemia, who are being considered for femoro-popliteal bypass surgery.

#### 5.1.1. Patient Inclusion Criteria

- 1. Patients with disabling symptomatic peripheral arterial disease
  - a. Rutherford stage 4 or 5 who require femoro-popliteal bypass surgery or
  - b. Rutherford stage 3 with severe claudication (less than 50 yards AND causing severe impairment of ability to work or undertake social activities)
- 2. ABI  $\leq$  0.6 in the study leg
- 3. Patient has failed adequate medical therapy which included
  - a. Exercise program
  - b. Smoking cessation therapy
  - c. Control of diabetes, hypertension and dyslipidemias
  - d. Antiplatelet therapy
- 4. Preoperative angiography or CT angiography shows superficial femoral artery occlusion AND required Humacyte HAV length of ≤ 38 cm. This imaging may have been conducted up to 6 months prior to study entry (Day 1) provided that the patient's symptoms have remained stable since that time
- 5. Preoperative imaging shows at least one below knee vessel patent to the ankle with good runoff
- 6. Proximal HAV anastomosis is expected to be to the common femoral artery below the inguinal ligament or to the superficial femoral artery
- 7. Distal anastomosis is expected to be to the popliteal artery above the knee
- 8. Femoral artery occlusion is not considered suitable for endovascular treatment; e.g. long segment chronic total occlusion, previous failed stent or stent graft in the superficial femoral artery, previous failed endovascular treatment where the lesion could not be crossed
- 9. Autologous vein graft is not feasible in the judgment of the treating surgeon; e.g. because all suitable veins have been used previously for coronary or peripheral bypass, or pre-operative vein mapping shows inadequate length or quality of vein to complete the planned bypass
- 10. Aged 18 to 85 years old, inclusive
- 11. Hemoglobin  $\ge$  10 g/dL and platelet count  $\ge$  100,000/mm^3 at screening

- 12. Other hematological and biochemical parameters within a range considered acceptable for the administration of general anesthesia at screening
- 13. Adequate liver function, defined as serum bilirubin ≤ 1.5 mg/dL; and international normalized ratio (INR) ≤ 1.5 at screening
- 14. Able to communicate meaningfully with investigative staff, competent to give written informed consent, and able to comply with entire study procedures
- 15. Life expectancy of at least 1 year

#### 5.1.2. Patient Exclusion Criteria

- 1. Limb at high risk of amputation (SVS WIfI [Society for Vascular Surgery: Wound, Ischemia, and foot Infection] stage 4)
- 2. Recent clinically significant trauma to the limb receiving the HAV
- 3. Severe active infection (SVS foot infection grade 3) in the limb receiving the HAV
- 4. Distal anastomosis planned to a below the knee artery
- 5. History or evidence of severe cardiac disease (New York Heart Association [NYHA] Functional Class III or IV), myocardial infarction within six months prior to study entry (Day 1), ventricular tachyarrhythmias requiring continuing treatment, or unstable angina
- 6. Stroke within six (6) months prior to study entry (Day 1)
- 7. Chronic renal disease such that multiple administrations of contrast agents may pose an increased risk of nephrotoxicity (eGFR < 45 mL/min)
- 8. Uncontrolled diabetes (HbA1c >10% at screening)
- 9. Treatment with any investigational drug or device within 60 days prior to study entry (Day 1)
- 10. Cancer that is being actively treated with a cytotoxic agent
- 11. Acquired immunodeficiency syndrome (AIDS) / human immunodeficiency virus (HIV) infection
- 12. Documented hypercoagulable state as defined as either:
  - a) a biochemical diagnosis (e.g. Factor V Leiden, Protein C deficiency, etc.) OR -
  - b) a clinical history of thrombophilia as diagnosed by 2 or more spontaneous intravascular thrombotic events (e.g. DVT, PE, etc.) within the previous 5 years
- 13. Spontaneous or unexplained bleeding diathesis clinically documented within the last 5 years or a biochemical diagnosis (e.g. von Willebrand disease, etc.)
- 14. Ongoing treatment with vitamin K antagonists or oral direct thrombin inhibitors or factor Xa inhibitors (e.g. dabigatran, apixaban or rivaroxaban)
- 15. Previous arterial bypass surgery (autologous vein or synthetic graft) in the operative limb
- 16. Stenosis of > 50% of the inflow aortoiliac system ipsilateral to the index leg. Any such stenosis must be corrected with angioplasty with or without stenting prior to, or at the time of, HAV implantation

- 17. Active autoimmune disease symptomatic or requiring ongoing drug therapy
- 18. Active local or systemic infection (white blood cells [WBC] > 15,000/mm^3)
- 19. Known serious allergy to aspirin
- 20. Any other condition which in the judgment of the investigator would preclude adequate evaluation of the safety and efficacy of the Humacyte HAV
- 21. Previous exposure to HAV
- 22. Employees of the sponsor or patients who are employees or relatives of the investigator
- 23. Pregnant women or women planning to become pregnant (women of child bearing potential [WOCBP] must use adequate contraception [hormonal or barrier method of birth control; abstinence] for the duration of study participation; WOCBP defined as not sterile or not > 1 year postmenopausal.)

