# 7. STUDY PROCEDURES / EVALUATIONS

# 7.1. Clinical Evaluations Through Month 12

- Medical History: at screening and Day 1, from patient interview and medical records covering relevant past medical history with particular reference to peripheral arterial disease, prior surgical or percutaneous procedures for PAD, other cardiovascular disease and concurrent medical conditions. Failure of optimum medical therapy for PAD should be documented.
- Smoking history and smoking cessation therapy: at screening and Day 1
- PAD symptoms assessment: at screening and all follow up visits from Day 29 onward through Month 12 using the VascuQol instrument (Morgan MBF et al 2001)
- Review of medications: at all study visits; prescription medication and non-prescription aspirin from Day -7 onward (see Section 6.7). Particular attention should be paid to the identification of over-the-counter (OTC) medications containing aspirin.
- Physical Exam: full exam at screening and Month 12 visit or final study visit for early termination (ET). Focused vascular clinical examination of the operative limb (including any ischemic lesions) and HAV at all post-operative visits; physical exam for lymphadenopathy at Day 5 and Day 29; additional clinical exam as needed to evaluate AEs.
- ABI (supine after 5 minute rest): at screening and all follow up visits from Day 29 onward through Month 12
- 6 minute walk test: at screening and at Months 3 and 12
- Vital signs (temperature, heart rate and sitting blood pressure): at screening and all subsequent study visits through Month 12
- Adverse events: post-operatively on Day 1 and all subsequent study visits; the patient will be asked a general question about his/her health and for any HAV problems since the previous visit.
- Angiography / CT angiography: this is a standard part of the pre-operative assessment of PAD patients. Patients should not be considered for the study unless results of a recent (within the 6 months prior to the screening visit and with no significant clinical deterioration subsequently) study are available.
- Vein mapping: this is a standard part of the pre-operative assessment of PAD patients. Patients should not be considered for the study unless results of a recent (within the 6 months prior to the screening visit) are available and indicate the absence of a suitable conduit for autologous vein bypass grafting.
- CT angiography to assess HAV anatomy at Day 29 and Months 6 and 12

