### 7.5. Study Schedule

#### 7.5.1. Screening (Day -35 to Day -1)

Potential study participants who are being considered for femoro-popliteal bypass surgery will be informed about the study and invited to participate. After explanation of the potential risks and benefits of the HAV and of the study procedures, written informed consent will be obtained. No study specific procedures may be performed prior to patient consent.

The following assessments will be performed within 35 days prior to surgery (Day 1):

- Informed consent
- Medical history
- Review of medical therapy for PAD (exercise program; antiplatelet therapy; management of diabetes, hypertension and dyslipidemias to current guidelines; smoking history and assistance with smoking cessation)
- PAD symptoms (VascuQol)
- Prior and concomitant medications (all prescription medications plus non-prescription aspirin)
- Full physical examination including number, size and location of ischemic lesions on the intended implant leg
- Evaluation of inclusion/exclusion criteria
- ABI measured with patient supine after 5 minutes rest
- 6 minute walk test
- Vital signs (blood pressure, heart rate, temperature oral, axillary or tympanic)
- Review of recent angiography / CT angiography (within previous 6 months and no significant clinical change since then) to confirm length of stenosis / occlusion of superficial femoral artery, length of required HAV and patency of run-off vessels
- Review of vein mapping to confirm absence of suitable autologous conduit
- ECG (12-lead)

- Laboratory testing
  - Hematology: full blood count and differential
  - Clinical chemistry; sodium, potassium, calcium, BUN, creatinine, albumin, total bilirubin, glucose (non-fasting)
  - Urine or serum HCG pregnancy test for WOCBP
  - Coagulation tests: aPTT and INR
  - HbA1c
  - PRA (sample to be taken for later analysis)

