1.3 Visit Terminology

Notation used in eCRF and protocol	Notation used for table, listing and graph presentation	Notification for treatment phases
Visit 1 (Screening, Day -35 to -1)	Screening	Screening
Visit 2 (Day 1)	Day 1	HAV implantation
	Baseline ¹	
Visit 3 (Day 5)	Day 5	Follow-up
Visit 4 (Day 29), ± 4 days	Day 29	
Visit 5 (Month 3), ± 14 days	Month 3	
Visit 6 (Month 6), ± 14 days	Month 6	7
Visit 7 (Month 9), ± 14 days	Month 9	7
Visit 8 (Month 12/ET), ± 14 days	Month 12	
Unscheduled	Unscheduled	
Every 6 - 12 months through Month 60 (± 30 days) at "standard of care" clinic visits	SOC Visit 1 to 10	Additional follow up

¹ The closest non-missing value prior to surgery on Day 1 will be used as baseline value. ET = Early Termination

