3.4 Interim Analysis

Data Monitoring Committee (DMC) reports will be provided during the course of the study.

Statistical Analysis Plan	Final Analysis
CLN-PRO-004	11/23

Endpoints will be assessed over a period of up to 60 months after HAV implantation.

- The **primary analysis** of the study will be based conducted on the earlier of a) when the final patient enrolled reaches 12 months post-implant or b) all subjects enrolled in the initial 36 month accrual period have reached 12 months post-implant. The SAP will call this the 1-year analysis.
- The **final analysis** will occur at the end of the study, when all patients have completed or exited the study.

The database extraction for the **1-year analysis** will include all study data collected at the time of the database extraction. The by-visit tables and figures will display all time points present in the data, including visits after the Month 12 visit (where applicable). Event tables (such as concomitant medications, AEs), will include all events during the study. Listings will display all study data available, including data collected after the Month 12 visit.

The database for the final analysis will include all study data and by-visit tables will display all study timepoints.

4 Statistical Evaluation

All tables, figures and listings will be produced using SAS (v9.4 or a more recent version).

Unless otherwise stated, categorical data will be presented using counts and percentages, whilst continuous parameters will be summarized using standard summary statistics as appropriate (n, mean, standard deviation [SD], median, minimum, maximum, 25th percentile, and 75th percentile). Minima and maxima will be quoted to the number of decimal places as recorded in the case report form (CRF); means, SDs and medians will be quoted to one further decimal place.

The closest non-missing values prior to implantation on Day 1 will be used as baseline values.

Unless otherwise stated, all confidence intervals will be presented as 95% two-sided intervals. For categorical endpoints, if all values are either success or failure, the exact CI will be presented.

As no sample size assessment has been undertaken, all analysis results are considered to be exploratory.

Details on the specification, definition, calculation and analysis of the efficacy and safety endpoint variables are given in Section 2 and the following sections.

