4.4.2 Analysis of Secondary Efficacy Parameters

Patency of the HAV (primary, primary assisted, secondary) rates will be presented for Months 3, 6 and 9.

Clopper-Pearson CIs will be presented for frequency counts of patency rates.

The HAV interventions and type of interventions needed to maintain / restore patency in the HAV through Month 12 will be descriptively summarized. Interventions will be recorded at each study visit and interventions occurring after the Month 12 visit will be provided in a listing.

Number of patients, who needed any intervention to maintain / restore patency throughout the study will be tabulated by counts and frequencies. The cumulative number of patients with any intervention needed will be presented stratified by visit and the number of patients having 1, 2, 3, etc. interventions will be presented.

Due to the nature of the study, an intervention can occur between planned study visits and will be recorded in the EDC as an unscheduled visit. A "by visit" summary will represent the intervention information that occurred before and on the scheduled visit. For example, the summary at Day 5 will denote the information from all interventions that occurred up to Day 5 visit and on the Day 5 visit. Similarly, the Day 29 summary will denote the information from all interventions that occurred after Day 5, and up to Day 29 (inclusive of Day 29).

VascuQol PAD symptom assessment data

The VascuQol PAD symptom assessment consists of 25 questions. The total score and the 5 domain scores (Activity, Symptom, Pain, Emotional, and Social) will be recorded in the clinical database. Total score and each domain score will be presented by descriptive measures for each visit as well as for the absolute change from baseline. Individual data, domain score and total score will also be listed.

The 1-year analysis will provide the table summary by planned visit up to Month 12. The final analysis will only display results in a listing.

ABI and 6 minute walk test

ABI and 6 minute walk test will be presented by descriptive measures for each visit as well as for the absolute change from baseline. Data will also be listed.

Statistical Analysis Plan	Final Analysis
CLN-PRO-004	16/23

The 1-year analysis will provide the table summary by planned visit up to Month 12. The final analysis will only display results in a listing.

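### For patients whose inflow stenosis is corrected after the baseline measurement, change in ABI, 6 minute walk and VascuQol mixes that procedure with the bypass, and the SAP does not show them separately

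*Protocol*

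**What the plan says.** **Eligibility.** Exclusion 16 (Protocol 5.1.2, repeated in the Protocol Summary) names a stenosis above 50% in the aortoiliac inflow on the study side, then adds: "Any such stenosis must be corrected with angioplasty with or without stenting prior to, or at the time of, HAV implantation". A corrected patient can therefore be enrolled. No timing relative to screening is set.

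**Measurement.** Protocol 7.1 schedules "ABI (supine after 5 minute rest): at screening and all follow up visits from Day 29 onward through Month 12" and "6 minute walk test: at screening and at Months 3 and 12". VascuQol follows the ABI schedule. Screening runs from Day -35 to Day -1 (Protocol 7.5.1). The list of pre-surgery assessments on Day 1 (Protocol 7.5.2) repeats none of the three, and Appendix 1 agrees.

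**Baseline.** SAP 1.3: "The closest non-missing value prior to surgery on Day 1 will be used as baseline value". SAP section 4 gives the same rule.

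**Analysis.** SAP 4.4.2: "ABI and 6 minute walk test will be presented by descriptive measures for each visit as well as for the absolute change from baseline". VascuQol is handled the same way. All analyses use the single safety set of HAV recipients (SAP 3.3).

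**Objectives.** Protocol 3.2 includes "To assess effect of the HAV on ABI", with matching wording for the walk test. For VascuQol the objective refers to the effect of implanting the HAV.

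**The concern.** A single-arm change score reflects everything done to the limb between the baseline and follow-up measurements. If the inflow is opened in that interval, the score covers two revascularizations, and the tables do not show which patients this concerns.

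The attribution matters because there is no comparator group (Protocol 6.1) and the protocol intends to set the results beside historical data on synthetic bypass grafts (Protocol 2.5.3). With no concurrent arm, an additional procedure cannot cancel out. If relieving an inflow stenosis adds to the ABI, as one would expect, the mean change overstates what the HAV contributed.

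**Working it through.** The plan states no figure on this point, and there is no sample-size calculation, effect size or standard deviation to reproduce. The check sets the eligibility, visit and baseline rules side by side. An illustration of size under stated assumptions follows.

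**Step 1: which value becomes baseline, by timing of the correction.**

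| Inflow corrected | Baseline under the SAP rule | What the change score contains |
|---|---|---|
| Before the screening measurement | Screening value, after correction | Inflow procedure is not part of the change |
| Between screening and Day 1, not re-measured | Screening value, before correction | Inflow procedure and bypass |
| Between screening and Day 1, re-measured at an unscheduled assessment | The later value | Inflow procedure is not part of the change |
| During the implant operation | Screening or later pre-operative value, necessarily before correction | Inflow procedure and bypass |

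The second and fourth rows are the problem. In the fourth, no pre-implant value after correction can exist.

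**Step 2: does anything in the SAP separate these patients?**
- SAP 4.4.2 gives unadjusted change in one analysis set.
- SAP 3.2 allows subgroup analysis, but as an option, for the main efficacy parameters, and without naming inflow correction.
- SAP 4.3 puts PAD interventional history and the surgery record in listings. Neither feeds the change tables.

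**Step 3: possible size for ABI.** Inputs:
- n = 15 patients recruited (SAP 1.5), taken as all implanted and all measured.
- k = patients corrected after baseline. Not in the documents; assumed 0 to 5.
- d = mean ABI change added by the inflow procedure in those patients. Not in the documents; assumed 0.05 to 0.3.

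Shift in the mean change = k × d / n.

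| k | d = 0.05 | d = 0.1 | d = 0.2 | d = 0.3 |
|---|---|---|---|---|
| 0 | 0 | 0 | 0 | 0 |
| 1 | 0.003 | 0.007 | 0.013 | 0.020 |
| 3 | 0.010 | 0.020 | 0.040 | 0.060 |
| 5 | 0.017 | 0.033 | 0.067 | 0.100 |

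For example, 3 × 0.2 / 15 = 0.04 and 5 × 0.3 / 15 = 0.10.

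**Step 4: relative size.** If the bypass alone gave a mean gain of 0.30 (assumed), the inflow share of the observed mean would be shift / (0.30 + shift). With k = 1 and d = 0.05 this is 0.003 / 0.303, about 1%. With k = 3 and d = 0.2 it is 0.04 / 0.34, about 12%. With k = 5 and d = 0.3 it is 0.10 / 0.40 = 25%.

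**Step 5: chance that anyone is affected.** If each patient has probability p of a correction after baseline, the chance of at least one among 15 is 1 − (1 − p)^15. For p of 5%, 10%, 20% and 30% (assumed) this gives 54%, 79%, 96% and more than 99%. At p = 5%, the chance that nobody is affected is still 46%.

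The documents offer no basis for a similar range for the walk test or VascuQol.

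**The case against.** The strongest reply is that this is a minor matter of reporting in an exploratory study.

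- **Nobody may be affected.** Correction before screening is allowed and causes no difficulty. This stands: zero belongs in the range. A reader might infer that the three endpoints are biased in favour of the HAV. The documents do not support that as a fact. It needs at least one affected patient and a positive added gain, and neither is shown.
- **The SAP makes no causal claim.** It plans descriptive summaries, there is no hypothesis test, and all results are called exploratory. This largely stands. A reader might infer that the SAP assigns the whole change to the HAV. It does not say so. The attribution comes from the wording of the objectives, which the tables are there to answer.
- **The baseline rule already handles re-measurement.** This stands. A value taken after correction and before implantation would be used automatically. It does not help with an intraoperative correction, or where nobody re-measured.
- **The listings allow a cross-check.** With 15 patients, a reader could match surgery and history listings against ABI values. This reduces the consequence but is not a planned display, and anyone given only the summary tables cannot do it.
- **Dropping these patients from the headline would be a poor trade.** This stands. With 5 excluded, at most 10 remain, selected on inflow disease. The all-patient summary should stay the main result.

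A reader might also infer that a net ABI gain could conceal an occluded HAV. It could sit beside one in these tables, but occlusion is captured by the patency endpoints.

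**Conclusion.** The point holds as one of attribution. The plan permits inflow correction after the baseline measurement, makes a combined change score unavoidable when correction is intraoperative, and neither counts nor separates the patients concerned.

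The size is unknown. Under the assumptions above, the mean ABI change shifts by 0 to 0.10: negligible with one patient and a small gain, material with five and a large one. That range rests on assumed values of k and d, on d being an addition to the bypass effect (additivity is not established), and on all 15 patients contributing.

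The consequence is confined to three secondary, exploratory endpoints. Patency, stenosis and the primary safety endpoints are not change scores from this baseline. This is a worthwhile, inexpensive improvement and not a defect in the main results.

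**What to change.** In SAP 4.4.2:

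1. Define a flag for any patient whose ipsilateral inflow was corrected between the baseline measurement and the end of the implant operation. Derive it from PAD interventional history, the Day 1 update of medical history, and the surgery record.
2. Report the number flagged, including when it is zero.
3. Keep the summary in the full safety set as the main result. Add a sensitivity column without flagged patients to the by-visit tables of change in ABI, 6 minute walk and VascuQol.
4. Describe the change in flagged patients as the effect of the combined revascularization.

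The baseline rule needs no change. No visit, measurement or clinical rule is altered.

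The cost is one derived flag and one extra column in three sets of tables, with a smaller n in that column. The flag depends on the date of the inflow procedure being recorded. The documents do not show a dated field for it, so this should be confirmed against the eCRF first.
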